14.2 STUDY EVALUATIONS

14.2.1 Clinical response evaluation

For evaluation of clinical responses, appropriate measures to accurately assess the presence of leukemic blasts in bone marrow or blood will be performed at indicted time point throughout the study (Table 1).

MRD will be assessed in bone marrow samples and Leukaemia Associated Immunophenotypes (LAP) will be established at start of the protocol. These cells will be followed during treatment and the MRD will be reported as %LAP positive cells of the WBC.

14.2.2 Assessment of MRD

MRD will be monitored in bone marrow aspirates by multiparameter flow cytometry assay according to standardized procedures. Bone marrow aspirate samples (at least 3 ml or 16.10E6 cells) will be collected in heparin coated tubes and will be send directly to the central lab at VUmc according to predefined and established procedures (Described in the Laboratory Manual). Samples will be processed according to standardized operating procedures and analysed using standardized gating strategies.

An additional bone marrow aspirate sample of 10 mL, taken at the same time as the analysis sample, will be biobanked according to local biobank laws. Materials will be stored as additional MRD analysis may appear to be relevant at a later stage. Which analyses to be performed will be decided later and will be dictated by the MRD analysis outcome. Samples will only be biobanked if the patients have consented to biobanking.

14.2.3 Assessment of Safety

Safety and tolerability will be assessed throughout the study starting from the time the patient signed the informed consent form until their participation in the study is finalized.

The safety parameters assessed throughout the study include physical examinations, vital signs, ECG recordings, laboratory evaluations (hematology, biochemistry, urine analysis) and recoding of Adverse Events. Throughout the duration of the study, adverse events and concomitant treatments will be recorded continuously.

14.2.3.1 Physical Examination

A general physical examination, including ECOG status, height (only at the screening visit) and body weight, will be performed during the study at different visits according to the assessment schedule presented in the study flowchart (Table 1). All laboratory results and assessment of abnormal results (clinical significance) will be recorded in the eCRF. The physical examination will include the following: head and neck, eyes, ENT (ears, nose, throat), heart, lungs, chest, abdomen, skin, musculoskeletal, neurological, endocrine and lymphatic system.

The physical examination performed at the screening visit will also include the ZUBROD-ECOG-WHO Performance status (see APPENDIX A) and the result will be recorded in the eCRF.

Vital signs measurements will be performed after at least 5 minutes of supine rest and will be recorded in the eCRF.

14.2.3.2 Electrocardiogram

ECG recordings will be performed at the screening visit. ECG recording parameters, and investigator assessment will be recorded in the eCRF.

14.2.3.3 Chest X-ray

A postero-anterior chest X-ray will be performed at the screening visit. Only abnormal clinically relevant findings will be recorded in the eCRF.

14.2.3.4 Laboratory Evaluations

Laboratory evaluations (hematology, biochemistry, urine analysis) will be performed at the local institute's laboratory. The following laboratory values will be assessed:

- Hematology: Hemoglobin, Ht, erythrocytes, reticulocytes, platelets, WBC and differential
- Blood chemistry: Na, K, creatinine, Ca, P, Mg, bilirubin, AF, GT, ASAT, ALAT, LDH, glucose, APTT, INR, fibrinogen.
- beta hCG blood test in woman with child-bearing potential
- Viral blood test (HIV, Hepatitis B and C)
- Urine analysis (pH, protein, erythrocytes, leucocytes, glucose, ketones, nitrites)

14.2.4 Assessment of Immune responses

DCP-001 vaccination supposed to develop anti-tumour activity in AML patients by inducing functional T-cell responses against tumour-associated peptides (TAA) derived from WT-1, RHAMM, Mucin-1 and PRAME that have shown to be important targets in AML and are presented by DCP-001. Monitoring the immune response is an essential element to evaluate efficacy. The analysis of the immune response against tumour antigens in blood samples from these patients before and after treatment allows a better understanding of 1) the underlying mechanisms of action of the immunotherapy 2) the prognostic value of immunological parameters and 3) the use of new knowledge about immune parameters to design improved immunotherapy treatments for the future. The following activities will be performed.

- a. Antigen-specific T cell mediated immunity will be measured in PBMC by IFN- γ ELISpot and intracellular cytokine release against antigens present in leukemic blasts and also known to be expressed by DCP-001 (i.e. PRAME, WT-1, MUC1, RHAMM). Both pre-and various time points post-vaccination will be analysed. In those patients that show positive responses, additional intracellular cytokine staining's (ICS) will be performed
- b. Changes in profiles of different PBMC populations. This includes T-cell profiles, regulatory T cells, MDSC, NK cells etc, according to the same schedule as for antigen-specific responses.
- c. General T-cell activation capability and thus immune competence of patients will be analysed by measuring T-cell proliferation and cytokine release following stimulation with DCP-001 in vitro. Pre- and post-vaccination samples will be compared.
- d. Biopsies will be taken from the injection side and analysed for specified markers by immunohistochemistry in order to identify the local immune infiltration process.

The assessment of the immune responses will be performed by a central lab, i.e. Immatics Biotechnology (www.immatics.com). Immatics is a leading cancer immunotherapy company and the global leader in the discovery of novel targets for various types of cancer immunotherapies.

Immunohistochemistry will be performed by DIAPath at the Center for Microscopy and Molecular Imaging (CMMI) at Gosselies, Belgium.

14.2.4.1 Sample collection, shipment and storage

Blood samples will be taken at indicated Visits (Table 1) from all patients included in the trial.

At the clinical site, a 70 mL heparin blood sample will be collected aseptically. Heparin blood is then transported immediately to the lab that performs PBMC isolation and cryoconservation for the site ('PBMC lab'). Trained and released PBMC operators will separate PBMCs (lymphocytes and monocytes) from other blood components (serum, erythrocytes, thrombocytes and granulocytes), count and freeze isolated cells according to Immatics SOP TC-021 within a total time of 8 h. All critical consumables will be provided by Immatics, including PBMC Kits containing components for isolation, freezing and cryopreservation. Labelling stickers allowing unambiguous identification of each cryovial. Isolation and cryopreservation will be documented in PBMC process slips that will be faxed/mailed to Immatics according to SOP TC-021. PBMC samples will be stored at -80°C for a maximum of one week and then transferred to LN2 tanks. Samples are sent to Immatics on dry ice by a trained courier service. Frozen PBMC samples will be transferred into a gas phase liquid nitrogen cryostorage system until in-house assays will be performed. Sample entry is regulated by Guideline GL-ADM003 and SOP IN-008. Immatics' cryostorage system is internally temperature controlled and additionally monitored by an electrical alarm system.

Biopsies (skin) will be taken via punch biopsies from the injection site 2 days after the first vaccination, 4th vaccination, and the second booster vaccination. Tissue samples must be handled as described in Laboratory manual. In short, samples must be fixed during at least 24 hours in a solution of formaldehyde 4% neutral pH (buffered) (maximum 48 hours of fixation). The volume of the fixative solution must be min 20x higher than the volume of tissue. After tissue fixation, samples will be directly sent to the central lab for further processing and immunohistochemistry analysis.

14.2.4.2 IFN- γ ELISPOT Assay

Principle

ELISpot assays are single-cell based and result in a parameter (the frequency of spot forming cells among mononuclear cells) that is expected to be correlated to the true frequency of activated antigen specific T lymphocytes in blood samples. As such assays also allow the processing of large numbers of samples and antigens in parallel, they have been widely used for immunomonitoring studies in a large number of clinical trials.

Description

In order to quantitatively determine the IFN- γ secretion by PBMCs isolated from peripheral blood samples a precise and accurate IFN- γ Elispot assay has been successfully developed and validated during two clinical trials performed by Immatics (IMA901-101 and IMA901-202). The assay is optimized with respect to the pre-sensitization conditions (medium, human serum, antigen concentration, duration), as well as readout conditions (antigen concentration). Thresholds for positive responses are defined by three criteria: 1) t-test (antigen triplicate vs. negative control triplicate), 2) ratio for mean of antigen vs. mean of negative control spots > 2.0 and 3) mean of antigen triplicate of spots per effector cells must be at least 6.0.

Statistical analysis for T-cell responses

Here, criteria for detection of above-threshold responses at given time points in a particular assay are defined. Those T-cell responses may be either vaccine-induced or due to other influences such as activated or naïve T cells prior to therapy.

Criteria for identification of above-threshold T-cell responses from ELISpot data are based on the recommendations of the CIMT Immunomonitoring panel (19). Further criteria increasing the stringency of the CIMT criteria were included to exclude the possibility of detection of false-positive responses.

Criteria for vaccine-induced T-cell responses in amplified Elispot assays

1. Criterion 1: Positive above-threshold immune response in a post-vaccination time point.
2. Criterion 2: For ELISpot assays, Rpost must be at least 2.0x of Rpre. Rpost and Rpre are the ratios at post- and pre-vaccination for the same antigen, patient & assay, for mean of antigen vs. control (triplicate of spots per 150.000 effector cells).

Note 1: If the criterion 2. cannot be calculated due to division by zero, 0.1 spot per 150.000 effector cells is added to all wells of pre-vaccination time point for that patient / assay combination and 2. is recalculated.

Note 2: If the criterion 2. cannot be calculated due to the flag for "too numerous to count", the respective well will be set to 1000 spots per 150.000 effector cells for the same assay and 2. is recalculated.

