14.2.4.3 ICS Assay

Principle

The Intracellular Cytokine Staining (ICS) assay has the capability to detect multiple effector functions, including IFN-gamma. It has been shown that such assays allow the detection of several cytokines and other functionalities at the same time on the same cell, and have been suggested as optimal for the sensitive and quantitative assessment of antigen-specific T cells in vaccination trials if multiple effector functions should be measured.

Description

In order to analyse the functionality and therefore the quality of T-cell responses a sensitive, quantitative ICS assay was developed which allows immunophenotyping of responding cells and measurement of multiple effector functions on a single cell level. This ICS assay has been validated during four clinical trials (IMA901-202, IMA910-101, IMA901-301, IMA950-101). The assay is optimized with respect to the pre-sensitization conditions (medium, human serum, antigen concentration, duration), as well as readout conditions (cells per well, antigen concentration, restimulation, antibody titrations and staining conditions). Thresholds for positive responses are defined by 3 criteria: 1) Positivity of at least one functional pattern (T cells expressing one of the functional markers, e.g. IFN- γ , TNF α , CD154, IL-10, IL-2, IL-4 or IL-5), 2) Frequency of functional T cells for an antigen must be at least 4x the frequency of the MOCK control for the same functionality and 3) Fisher exact test (two-sided) for counts of functional T cells and non-functional T cells for antigen vs. MOCK control must be $p < 0.001$.

Statistical analysis for T-cell responses

Criteria for identification of above-threshold T-cell responses for the ICS assay are based on ELISpot criteria.

Criteria for vaccine-induced T-cell responses in amplified ICS assays

1. Criterion 1: Positive above-threshold immune response in a post-vaccination timepoint.
2. Criterion 2: For ICS assays, Dpost must be at least 4 x Dpre. Dpost and Dpre are the differences of T-cell frequencies at post- and pre-vaccination for the same antigen, patient & assay, for antigen minus HIV-001 control.

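### The ELISpot zero-count correction (section 14.2.4.2, Note 1) leaves some samples unclassifiable and can turn a clear rise into a non-response

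*Protocol*

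**What the plan says.** Section 14.2.4.2 sets two conditions for a vaccine-induced ELISpot response.

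- Criterion 1 is a "Positive above-threshold immune response in a post-vaccination time point". Positivity combines a t-test of antigen against control triplicates, a "ratio for mean of antigen vs. mean of negative control spots > 2.0", and a minimum count: "mean of antigen triplicate of spots per effector cells must be at least 6.0".
- Criterion 2 is a fold change: "For ELISpot assays, Rpost must be at least 2.0x of Rpre". Each R is a ratio "for mean of antigen vs. control (triplicate of spots per 150.000 effector cells".

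Note 1 deals with zeros: "If the criterion 2. cannot be calculated due to division by zero", then "0.1 spot per 150.000 effector cells is added to all wells of pre-vaccination time point for that patient / assay combination" and the criterion is recalculated. Note 2 covers only wells too numerous to count. No rule addresses a zero control mean after vaccination, either in criterion 2 or in the positivity ratio.

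The ICS rule in section 14.2.4.3 has a different form: "For ICS assays, Dpost must be at least 4 x Dpre", where D is antigen minus control, so no division by a control count arises.

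Immune response is a primary objective (section 9.1.1) and appears under the primary efficacy endpoint (section 9.2.1).

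**The concern.** Note 1 changes only one side of the comparison, and the constant it adds is very small. A correction for zeros should make every sample classifiable and should not let the call depend on whether a stray control spot appeared. This one does neither in all cases.

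At stake is the responder flag of an antigen-specific assay. The groups are planned at 10 patients each (section 16.1), so one patient whose flag is missing or wrong moves a group's response rate by 1/10, or 10 percentage points. Section 14.2.4 also makes additional ICS testing depend on a positive response, so an undefined positivity call could affect who is tested further.

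**Working it through.** Notation: antigen/control are triplicate means in spots per 150,000 effector cells. R = antigen/control. Criterion 2 is met if Rpost ≥ 2.0 × Rpre. Note 1 adds 0.1 to the pre-vaccination means only. A zero mean requires all three wells to be zero. The protocol states no result to reproduce, so the rule is applied as written to illustrative counts.

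**Case (i): post-vaccination control mean is zero.** Pre 3/1, post 50/0.
- After Note 1, Rpre = 3.1/1.1 = 2.82.
- Rpost = 50/0, unchanged, because Note 1 leaves post-vaccination wells alone. Criterion 2 cannot be evaluated.
- The positivity ratio in criterion 1 is also 50/0, with no rule for it.

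**Case (ii): pre-vaccination control mean is zero, with antigen mean A before vaccination.**
- After Note 1, Rpre = (A + 0.1)/0.1 = 10A + 1.
- Pre 8/0, post 100/1: Rpre = 81, Rpost = 100, needed 2 × 81 = 162. Not induced, although net spots rise from 8 to 99.
- Pre 8/1, post 100/1: Rpre = 8, Rpost = 100, needed 16. Induced, with 100/8 = 12.5. One baseline control spot reverses the call.
- With a baseline below the 6-spot minimum, pre 3/0, post 50/1: Rpre = 31, Rpost = 50, needed 62. Not induced. Post wells of 45, 50, 55 against 1, 0, 2 meet all of criterion 1 (t-test p = 0.00008, ratio 50, mean above 6).

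**Where the rule works.** Pre 0/0, post 20/1: Rpre = 0.1/0.1 = 1, Rpost = 20, needed 2. Induced.

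**Which feature causes case (ii).** Adding 0.1 at both time points still gives pre 81 and post 100.1/1.1 = 91, below 162. Adding 1 at both gives pre 9/1 = 9 and post 101/2 = 50.5, above 18. The main cause is the size of the constant inside a ratio of ratios; one-sidedness alone explains only case (i).

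**How often.** The protocol gives no background count, so the range below is assumed: Poisson background of mean m per well, the same before and after vaccination. The chance of an all-zero control triplicate is exp(−3m). The last two columns are criterion 2 with Note 1 on simulated triplicates, for a true net rise from 3 to 30 spots; criterion 1 was not simulated.

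| m (assumed) | All-zero triplicate | Undefined | Negative |
|---|---|---|---|
| 0.25 | 47% | 47% | 10% |
| 0.5 | 22% | 22% | 12% |
| 1 | 5% | 5% | 9% |
| 2 | 0.25% | 0.2% | 5% |
| 3 | 0.01% | 0.01% | 4% |

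At 1 spot or more per well, at least half of the negatives have non-zero controls at both time points. They are ordinary noise in a ratio with a small denominator and are not produced by Note 1.

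**The case against.** **Antigen over zero could be read as infinite.** It would then exceed any threshold, and case (i) becomes a wording gap. On that reading the existing rule calls 90%, 88% and 91% responders at 0.25, 0.5 and 1 background spots. This is a sensible reading, but the protocol does not adopt it; it prescribes an offset and a recalculation that cannot be carried out. It does nothing for case (ii).

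**The gap may be closed elsewhere.** Section 14.1 refers laboratory procedures to the Laboratory manual and section 16.2.4 refers analysis details to the SAP; neither is at hand. That could settle case (i). It does not excuse case (ii), because there the protocol itself fixes the offset and the time point.

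**Little depends on the flag.** Section 16.2 plans no inferential analysis, section 16.1 speaks of the effect on MRD as the primary endpoint, section 9.2 names no ELISpot responder rate, and immune data are to be summarised descriptively by group and visit. ELISpot is one of several immune assessments. This stands and lowers the weight of the point.

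**A reader might infer that the rule misses most true responders, or that the cleanest assays are generally misclassified.** Adding undefined and negative results together does leave only 43%, 66% and 86% called responders at 0.25, 0.5 and 1 background spots. At the two lower values most of the shortfall is undefined samples; at 1 spot about half of the negatives are ratio noise; at 2 to 3 spots zero triplicates nearly vanish. The document does not say which background applies. Case (ii) also depends on the counts, as the 0/0 baseline shows, and a baseline of 8 spots already reaches the 6-spot minimum, so a pre-existing response is plausible in that example. The 3/0 example is free of this.

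**Conclusion.** Note 1 is wrong as written and should be fixed. Both failures follow from the protocol's text and need no assumption: a zero post-vaccination control mean leaves criterion 2 and the positivity ratio undefined, and a zero pre-vaccination control mean with some antigen spots can turn a clear rise into a non-response. Their frequency is not known. Across the assumed backgrounds of 0.25 to 3 spots per well it runs from almost half of samples undefined to practically none.

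It would go too far to say that the primary analysis is invalidated. No test, power figure or error rate changes; the damage is confined to missing or wrong responder flags in a descriptive immune endpoint with small groups.

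**What to change.** In section 14.2.4.2, and in the SAP where it repeats the rule, before any sample is read out:

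1. Define criterion 2 on background-subtracted counts: (mean antigen − mean control) post ≥ 2 × max[(mean antigen − mean control) pre, floor], with the floor stated, for example 1 spot per 150,000 cells. The floor keeps a net baseline at or below zero from letting any small count pass.
2. Write the positivity ratio in criterion 1 as mean antigen > 2.0 × mean control, which is defined when the control is zero. Without this, case (i) persists in criterion 1.
3. Delete Note 1.

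Check on the examples: pre 8/0, post 100/1 gives 99 against 2 × 8 = 16, induced. Pre 3/1, post 50/0 gives 50 against 2 × 2 = 4, induced, and 50 > 2.0 × 0 holds.

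If the ratio must stay, add one stated constant of about 1 spot, not 0.1, to all wells at both time points in every patient, whether or not a zero occurs. Step 2 is still needed. In the same simulation at 0.25, 0.5 and 1 background spots, a symmetric 0.1 gives 85%, 86% and 92% responders; a constant near 1 gives 99% or more.

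The cost is one paragraph and no new data. Results become slightly less comparable with the laboratory's earlier trials, so show the present rule as a sensitivity analysis and report how many samples it leaves undefined.

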14.2.4.3 ICS Assay

Principle

The Intracellular Cytokine Staining (ICS) assay has the capability to detect multiple effector functions, including IFN-gamma. It has been shown that such assays allow the detection of several cytokines and other functionalities at the same time on the same cell, and have been suggested as optimal for the sensitive and quantitative assessment of antigen-specific T cells in vaccination trials if multiple effector functions should be measured.

Description

In order to analyse the functionality and therefore the quality of T-cell responses a sensitive, quantitative ICS assay was developed which allows immunophenotyping of responding cells and measurement of multiple effector functions on a single cell level. This ICS assay has been validated during four clinical trials (IMA901-202, IMA910-101, IMA901-301, IMA950-101). The assay is optimized with respect to the pre-sensitization conditions (medium, human serum, antigen concentration, duration), as well as readout conditions (cells per well, antigen concentration, restimulation, antibody titrations and staining conditions). Thresholds for positive responses are defined by 3 criteria: 1) Positivity of at least one functional pattern (T cells expressing one of the functional markers, e.g. IFN- γ , TNF α , CD154, IL-10, IL-2, IL-4 or IL-5), 2) Frequency of functional T cells for an antigen must be at least 4x the frequency of the MOCK control for the same functionality and 3) Fisher exact test (two-sided) for counts of functional T cells and non-functional T cells for antigen vs. MOCK control must be $p < 0.001$.

Statistical analysis for T-cell responses

Criteria for identification of above-threshold T-cell responses for the ICS assay are based on ELISpot criteria.

Criteria for vaccine-induced T-cell responses in amplified ICS assays

1. Criterion 1: Positive above-threshold immune response in a post-vaccination timepoint.
2. Criterion 2: For ICS assays, Dpost must be at least 4 x Dpre. Dpost and Dpre are the differences of T-cell frequencies at post- and pre-vaccination for the same antigen, patient & assay, for antigen minus HIV-001 control.

14.2.4.4 Treg / MDSC / PROFILE Assays

Principle

Characterisation of immune cell activation and effector phenotypes is an important measure of responses to immunotherapy. DCP-001 vaccination-induced changes in the frequency and/or activation status of different immune cell populations (e.g. T cells, NK-cells, regulatory T cells, Monocytes) will be determined for available patient PBMC, as these may be informative in further dissecting the nature of the response. Flow cytometry will be used to detect and quantify cells stained with fluorescently labelled antibodies. Additionally, other cell populations including but not restricted to regulatory T cells and myeloid-derived suppressor cells shall be determined by multicolour flow cytometry to investigate potential correlations with T cells responding to tumour-associated peptides derived from WT-1, RHAMM, Mucin-1 and PRAME

Description

In order to assess cellular biomarkers three different assays will be used: 1) a Treg assay (analysing regulatory T Cells), 2) an MDSC assays (analysing myeloid-derived suppressor cells) and 3) the PROFILE assay (analysing the profile of cells present in the PBMC compartment). The Treg and the MDSC assay have been developed for a clinical trial of Immatix (IMA901-202) and has been validated during 5 clinical trials. The PROFILE assay has been developed for this trial and will be used for the first time. The Treg and MDSC assays have been optimized in terms of antibody titrations, instrument settings, compensation and isotype controls. Validation has been assessed for intra-assay variability, inter-assay variability and accuracy.

